- 2. Evaluate whether aspects of the advocacy intervention experience thought to improve outcomes modify the effect of the advocacy intervention on mental health and wellbeing; in particular, to test whether
 - a. the effect changes as the amount of support received increases
 - b. the effect varies according to structural or service characteristics of NGOs;
- 3. Assess the service use and costs associated with advocacy interventions for trafficked people who have been referred into NGO services

8. (a) Study design

Exploratory prospective uncontrolled cohort study and realist evaluation with assessments at baseline (T1) (i.e. at or soon after onset of advocacy support), at 3 months follow up (T2) and at 6-months follow-up (T3). The primary outcome is reduced psychological distress (measured using the CORE-OM) at 3 months follow up (T2) compared with baseline (T1).

(b) Rationale for not including a control group

It is not feasible to recruit a control group for the following reasons: (1) All trafficked people who enter the National Referral Mechanism (NRM) are entitled to government-funded NGO support. Support is provided by a national network of NGOs; there is enough capacity, so NGOs do not operate waiting lists that could serve as a source of controls; (2) Trafficked people who enter the NRM but elect not to receive NGO support are extremely difficult to identify for recruitment. The PI's previous research showed that it is not feasible to recruit from settings such as the NHS and Local Authorities (4).

This study will therefore assess whether mental health among survivors of trafficking improve over the period during which advocacy support is provided, with measures taken at or soon after onset of advocacy intervention, at 3 months follow up, and at after a further 6 months follow up. To support the interpretation of any detected change as a causal intervention effect in the absence of a control group dose-response relationships between change over time and

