Staff - To be eligible for inclusion, staff must work (on a paid or voluntary basis) at one of the participating NGOs to be eligible for inclusion

Exclusion criteria

Individuals will be excluded from the study if they:

1. Do not have the capacity to provide consent to participate in the studies, including because of learning disability, psychotic illnesses or severe drug or alcohol problems.

Eligibility will be assessed by a trained KCL researcher.

11. Intervention

The intervention being evaluated is advocacy support as provided by NGOs during the study period. Advocacy interventions are multi-faceted and non-manualised, and the specific support provided varies according to service model (i.e. between NGOs) and to individual need (i.e. between participants). The intervention is delivered by NGO caseworkers.

The core components of advocacy interventions for this population, as identified by NGOs during work to develop initial programme theory, typically include:

- 1. Providing information about rights and support options
- 2. Offering encouragement, empathy, and respect;
- 3. Providing informal counselling and setting goals;
- 4. Increasing access to community resources and to housing and welfare support;
- 5. Increasing social support;
- 6. Building skills, including training, education, and life skills, and assistance to access employment.

In order to access the intervention, trafficking survivors must consent to be referred into the National Referral Mechanism (the "NRM" - a centralised system for identifying and referring trafficked people into government-funded support services). Individuals may not self-refer into the NRM but must be referred by a First Responder organisation.

Individuals who have been referred into the NRM undergo a two-stage decision-making process regarding their claim to have been trafficked. Decisions are made by a centralised Single Competent Authority and not by NGOs. An initial "reasonable grounds" decision is usually made within five days of referral into the NRM. This is a low threshold test which determines the person's status as a "potential victim of trafficking"; individuals in receipt of a positive reasonable grounds decision are then eligible to receive NGO support funded through the UK Victim Care Contract. Individuals will ordinarily have received a positive reasonable

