Validated translations for the above instruments are not available across all of the language groups expected to be represented in the study sample. Although a limited number of translations are available for some of the above instruments (e.g. the CORE-OM, the EQ-5D-5L) their quality is not considered to be high. Questions will therefore be translated by interpreters during interviews.

Additional baseline measures

Measures to be collected at baseline also include participant level socio-demographic and trafficking related factors that may modify the intervention effects or predict outcomes and so may act as confounders of the dose response relationships investigated by research questions 2 and 3. Measures that will be additionally collected at T2 and T3 are indicated by an asterisk. These are:

- 1. Gender
- 2. Age
- 3. Nationality
- 4. Immigration status*
- 5. Housing status*
- 6. Type of exploitation
- 7. Duration of exploitation
- 8. Time since exploitation

Process variables

NGOs routinely record participant-level data on the type, frequency, and duration of advocacy support, including number of sessions. These data will be extracted from client records and used to construct a measure of dose.

Study 2 – Qualitative Study

Data will be collected using qualitative semi-structured interviews. Interviews will follow topic guides; indicative topic guides are appended as supporting documentation. The topic guides will be finalised for piloting following review and feedback by participating organisations, the study steering committee, and the survivor research advisory group. The topic guides will be piloted with three survivor and three staff participants and then reviewed.

Interviews with survivors will explore, for example, which aspects of support made a difference to them, why, and how, and which were less helpful (mechanisms); and perceived changes in safety, risk, autonomy, social connectedness, unmet needs, and mental health and wellbeing attributable to advocacy support (outcomes) or to other circumstances; and what barriers and enablers they identify in the context of assistance for the service and for themselves in achieving improved safety, risk, autonomy, social connectedness, unmet needs, and mental health and wellbeing (context). Where survivors had less successful outcomes or experiences, interviews will explore opinions about what might have helped. Professional interpretation will be provided as required.

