Audio recordings of the qualitative interviews will be taken on encrypted digital recorders. Recordings will be transferred onto the secure internal university network with password-protected permissions. Audio files will then be removed from the recording device. Audio files will then be securely transferred to a professional transcription agency following signature of a confidentiality agreement. Transcripts will be downloaded to the secure internal university network and checked against the audio file: after checking, the audio file will be deleted from the university network/server. Transcripts will be anonymised during this checking process.

As per funder guidance, research data will be stored for 10 years after project completion.

19c Data access

Access to participants' personal data will be restricted to the study team (including NGO researchers, for the purposes of data collection and transfer, and Clinical Trials Unit staff), interpreters, transcribers, and auditors. The only exception to that is if a participant discloses something that leads the research team to believe that the participant or another person is at serious risk of harm. In this scenario, the researcher will explain to the participant that they need to break confidentiality to respond to the identified risk. This is detailed on the participant information sheet.

A confidentiality agreement will be in place with transcribers and interpreters.

20. Statistical methods

20a Statistical methods for analysing primary and secondary outcomes

To assess whether receipt of advocacy support is associated with improved mental health a paired samples t-test (or nonparametric equivalent) to assess mean change over the study period (6 months) will be conducted.

20b Methods for additional analyses

To assess whether change over times varies with intervention characteristics (amount of advocacy support received by study participant RQ2 or NGO service characteristics) change scores will be constructed over the intervention period.

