The "dose of the support received" will be quantified (e.g. duration in terms of session length, frequency, and the period over which sessions are received; structural and service characteristics NGOs) and change scores will be regressed on this dose. Possible confounders of the dose-response relationship will be identified by testing whether any baseline participant characteristics (e.g. gender, immigration status) predict change over time. Any such potential confounders will then be adjusted for in a second step which regresses the change changes on the dose variable and the putative confounders.

These analyses (which do not include a control group) are based on the assumption that a control group would not exhibit any change over the intervention period. In order to assess the

impact of departures from this assumption on the evaluation of the advocacy support intervention sensitivity analyses will be conducted. Literature evidence will be used to generate a possible distribution of mean outcome change in a hypothetical control group of eligible trafficked woman waiting to start the support program (37); and will then include such sensitivity parameters in our analyses models to study their impact on the estimation of the prepost effect.

20c Methods for handling missing data

In the case of missing data in the CORE-OM outcomes, putative baseline confounders, or process variables, multiple imputation (MI) will be used to ensure that the analyses remain valid under an appropriate missing at random assumption. This will enable us to (multiply) impute realistic outcome patterns including allowing for process variables such as discontinuation of advocacy support to drive loss-to follow-up.

21. Economic evaluation

An exploratory analysis of service use, costs and effects before and after intervention will be undertaken with the results presented using a cost consequences framework, which is recommended for the evaluation of complex interventions that have multiple effects (38). This work will be used to support the generation of recommendations for future research and the development and testing of economic measures appropriate for this population. Specific objectives will include the following:

- 1. Calculate the cost of the advocacy interventions taking a micro-costing (bottom-up) approach (38).

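### The dose-response analysis screens confounders by significance and leaves T1 CORE-OM unaddressed, so its slope is not safe evidence for the causal reading that Section 8(b) rests on it

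*Protocol*

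**What the plan says.** Section 20b sets out a two-step procedure. For the outcome, "change scores will be constructed over the intervention period". In the first step "change scores will be regressed on this dose". Covariates are then chosen by a test: "Possible confounders of the dose-response relationship will be identified by testing whether any baseline participant characteristics (e.g. gender, immigration status) predict change over time". Those that pass enter "a second step which regresses the change changes on the dose variable and the putative confounders".

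Section 12 (Additional baseline measures) describes "socio-demographic and trafficking related factors that may modify the intervention effects or predict outcomes and so may act as confounders" of the dose-response relationships. It lists eight: gender, age, nationality, immigration status, housing status, and type, duration and time since exploitation. CORE-OM is collected at T1 (Section 13), but the timetable labels it as the primary outcome, not as a baseline characteristic.

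Section 8(b) gives the purpose of the analysis: "To support the interpretation of any detected change as a causal intervention effect in the absence of a control group". Section 11 says of the intervention that "the specific support provided varies according to service model (i.e. between NGOs) and to individual need".

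**The concern.** A confounder is related to both dose and outcome. The screen looks only at the outcome, in the same data, and requires significance. A covariate strongly tied to dose but modestly tied to change will often be dropped, and its bias stays in the dose slope.

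The second issue is the T1 score itself. Change is partly determined by T1: people who score high at T1 tend to fall on re-measurement whatever they receive. If support goes to those who are more distressed at intake, dose and improvement become associated with no effect of dose.

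The stakes are high for this design. With no controls, the dose slope is the main internal evidence offered for causation, and Section 7 hypothesises that benefit is dose-dependent, which is what this bias would appear to confirm. The only sensitivity analysis in Section 20b varies the mean change of a hypothetical control group and addresses the pre-post effect. It does not touch the dose slope.

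**Working it through.** **Inputs from the protocol (Section 14).** 450 recruited, 25% lost by T2 and a further 25% by T3: 450 × 0.75 = 337.5 and 450 × 0.75² = 253.1, so n = 337 and n = 253. Both are used because Section 20b does not say which follow-up closes the intervention period. The SD is 18.

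**The plan's own figures.** The protocol states no figure for the dose-response analysis. Its pre-post figures reproduce: (1.960 + 1.282)/√337 = 0.177 against the stated 0.18, and (1.960 + 1.282)/√253 = 0.204 against the stated 0.20. In points, 0.18 × 18 = 3.24 and 0.20 × 18 = 3.6. They are not in dispute.

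**Assumptions.** The protocol gives neither the T1 to follow-up correlation (rho) nor the correlation of dose with T1 CORE-OM (c). Using SD = 18 for a paired difference implies 18 × √(2(1 − rho)) = 18, so rho = 0.5 if variances are equal; 0.7 is also shown. c is taken as 0.1, 0.2 and 0.3. Dose has no effect throughout.

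**A. Screening.** Assume eight independent confounders, each correlated 0.1 with change and 0.2 with dose, all pulling the same way. Unadjusted, the dose-change correlation is 8 × 0.1 × 0.2 = 0.16, a false slope of 0.16 × 18 = 2.88 points per SD of dose. By simulation, the screen picks each confounder in about 45% of samples at n = 337 and 35% at n = 253. False positives after screening are about 19% and 20%; with all eight always in the model they are about 5%. For scale, a single screened confounder correlated 0.10 or 0.15 with change and 0.3 or 0.5 with dose gives only 4.6% to 6.2%. The harm comes from several modest omissions adding up.

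**B. Dose follows the T1 score, including its transient part.** The false slope of change on dose is −(1 − rho) × c × 18. At rho = 0.5 it is −0.9, −1.8 and −2.7 points per SD of dose. The dose-change correlation is −c × √((1 − rho)/2), that is −0.05, −0.10 and −0.15. False-positive rates of the change-score model, as the span of analytic and simulated results:

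| | c = 0.1 | c = 0.2 | c = 0.3 |
|---|---|---|---|
| n = 337, rho = 0.5 | 14–15% | 44–45% | 78–80% |
| n = 253, rho = 0.5 | 12–13% | 33–36% | 66–67% |
| n = 337, rho = 0.7 | 11% | 29–30% | 56–58% |

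Adding T1 CORE-OM brings every cell to about 5%.

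**C. Dose follows stable underlying need.** Let T1 and follow-up share a stable component with independent fluctuation at each time, and let dose depend on the stable component only, with the same c. Change then contains no stable component, so its covariance with dose is zero and the change-score model holds about 5%. The baseline-adjusted slope is instead +c(1 − rho) × 18/(1 − c²): at rho = 0.5 it is +0.9, +1.9 and +3.0 points per SD of dose, falsely showing more support with less improvement. At n = 337 it rejects in about 18%, 58% and 92% of studies (rho = 0.5), or about 13%, 34% and 67% (rho = 0.7).

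**The case against.** The strongest counter-argument is case C, and it stands. Support follows a needs assessment and an individual plan (Section 11), T1 comes after planning has begun (Section 13), caseworkers may not interview their own clients (Section 15), and questionnaires stay within the study (Section 27). Caseworkers therefore do not allocate support on the T1 questionnaire score. Any link runs through distress or need at the time, and how much of that is transient is unknown. This is Lord's paradox: in non-randomised data, neither change scores nor baseline adjustment is right in general.

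A reader might infer that the plan as written will produce a spurious dose-response and that making T1 CORE-OM a mandatory covariate cures it. The documents do not support that. The cure works under mechanism B only. The sign of c is also open, because the plan categories in Section 11 are largely practical and a negative trafficking decision ends support whatever the distress. At c = 0 there is no bias of this kind; at negative c it reverses.

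A reader might also infer that T1 CORE-OM is barred from the second step. It is not clearly barred: the rule covers any baseline characteristic, and its two examples are only examples. If T1 CORE-OM were a candidate, the screen would pick it in essentially every simulated sample. But the Section 12 list and the Section 13 labels point the other way, so the text leaves its handling open.

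Finally, covariate details are often left to an analysis plan, which is not shown. That answers silence. It does not answer the screening rule, which the protocol states outright.

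**Conclusion.** The point holds in this form: Section 20b fixes a screening rule that performs worse than the plain alternative, and leaves open how T1 CORE-OM is handled in the analysis on which the causal reading rests.

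The screening result assumes eight independent confounders acting in the same direction; if some pull in opposite directions, the biases partly cancel. The T1 result depends on c, rho and, above all, on whether dose tracks transient distress or stable need. The protocol settles none of these, so the percentages show what could happen and are not predictions.

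This should be fixed before analysis. It is not a fatal flaw: the study is described as exploratory, this is an additional analysis, and the primary paired comparison is unaffected.

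**What to change.** In Section 20b, or in the analysis plan with a note that it supersedes Section 20b:

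- Drop the significance screen. Adjust for all eight Section 12 factors, fixed in advance, using T1 values of immigration and housing status and a pre-set grouping of nationality.
- Report the adjusted dose slope twice, with and without T1 CORE-OM as a covariate, and say which follow-up defines the change.
- Claim support for a causal dose-response only if both slopes point to benefit and both 95% intervals exclude zero. In B and C one of the two models holds 5% two-sided, so a false claim of benefit from this source is limited to about 2.5%.

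The cost is a few more model terms, affordable at 253 to 337 participants, and one extra reported model. All variables are already collected. The agreement rule is cautious: under mechanism C the baseline-adjusted slope is pulled against benefit, so a real effect may fail to meet it. Disagreement between the slopes should be reported as such, with the likely drivers of dose discussed.

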Participant Identification Numbers (PINs) are assigned to cohort study participants via the MACRO database after the T1 interview has been completed/terminated. After completing the interview, the NGO researcher should log into the MACRO database and complete the participant Registration Form. Completion of this form automatically generates a PIN. The PIN should be written in ink at the top of all sheets in the questionnaire pack and the questionnaire pack then securely stored as detailed below.

18i Retention

People recruited to the research may (a) drop out of the support programme; (b) drop out of

the research; (c) both. We will seek to retain participants in the research if they drop out of the support programme. As per section 16a, the KCL researcher will administer T2 and T3 questionnaires to participants who leave the recruiting organisation.

We will use several strategies to reduce drop out from the research based on the experience of the applicants and collaborators in conducting evaluations of complex interventions. These include:

- Asking participants to complete a contact details information sheet at baseline, including a contact telephone number and (if applicable) email address, plus a contact telephone number for a person they trust. The participant information sheet explains that we request the details of a trusted contact in case we are unable to get in touch with them at follow-up.
- Upon completion of T2, provision of a business card with the details of the Study Manager plus a stamped addressed envelope in case of change in contact details.
- Upon receipt of information following T2, the Study Manager will telephone the participant to introduce themselves, thank them for participating to date, and to let them know they will be in touch with them in three months' time to complete the final questionnaire. This additionally provides an opportunity to recheck contact details.
- Providing flexible follow-up appointments (see section 13 for details of data collection windows):
- Providing expenses to cover travel to appointments if required;
- Sending text message reminders at interview 1 week and 1 day prior to follow-up appointments;
- Maintaining contact between data collection points (e.g. thank you cards, newsletters);
- Providing multi-use shopping vouchers thank participants for their time.

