Access to the KCL site is highly restricted: key-locked cabinets are stored in key-locked offices, the doors to which are locked when research team members are not present. Access to office buildings and corridors is restricted to identity card holders by means of swipe card readers. Although the exact security arrangements of participating NGOs may vary between sites, access is also highly restricted due to the need to protect trafficked people from potential risk of harm and staff offices are locked when staff are not present.

Hard copy data may be transferred between the NGO and the university manually or using a signed for and tracked mail service. Manual transfers are scheduled for when the study PI or manager is visiting the site. The data should be signed out by the PI/post-doctoral researcher and counter-signed by a representative of the NGO. The data should be transferred into a padlocked bag and taken directly to the university site, where they must be signed in and securely stored.

If data are removed from the filing cabinet by a member of the research team (e.g. for data entry into the MACRO database) they must be signed out and signed back in upon return. Data must be returned to the filing cabinet if the researcher is leaving the office even if temporarily.

The departmental postal address for the location within the College at which research data will be stored during and after the study is as follows: [name].

Research data entered into the electronic MACRO database will be stored on the secure university network/server.

Project data (i.e. data routinely collected by the NGO) will be extracted by The Salvation Army for participants who have provided their consent. Extracts will be securely transferred from The Salvation Army to the research team using the KCL Secure File Transfer service and

downloaded to the secure internal university network/server. Data contained within the extract will be entered into the MACRO database and checked before deletion.

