Potential participants will be given a minimum of 24 hours to consider their participation in the study before consent is sought, and it will be emphasised that participation is voluntary. During the formal consent process, each participant will be informed that their responses will be anonymous and confidential (e.g., no names would be used on questionnaires, and questionnaires will not be seen by anyone outside the study), and that the study is not related to any immigration or policing procedures. Participants will be advised that they do not have to answer any questions, if they do not wish to, that they may take a break or terminate the interview at any time, and that declining to participate will not in any way affect the services they are receiving. Participants who decline to participate in the study will be asked if their basic socio-demographic characteristics (gender, age, and country of origin) can be collected anonymously to determine whether there are differences between participants and non-participants.

Only people who meet all inclusion criteria and no exclusion criteria and can provide informed consent will be recruited. Individuals who are interested to participate will be asked by NGO researchers to provide written consent. Prior to the administration of questionnaires, participants will be reminded that participation is voluntary and will not affect the service they receive, that they do not have to answer questions if they do not wish to, and that they can take a break or terminate the questionnaire at any time. Questionnaires will be administered only by trained individuals and in private.

28. Confidentiality and anonymity

The information provided by participants will be confidential and pseudo-anonymised. In some situations, however, it may be necessary to disclose personal information without a patient's consent if it is in the public interest (i.e. where a failure to do so may expose the patient or others at risk of death or serious harm). The limits of confidentiality are explained on the participant information sheet and will be discussed with all participants as part of the informed consent process.

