All participants will be assigned a unique PIN. PINs will be used at all times when managing the research data. Any data collected that includes identifiable details about study participants will be stored separately from the research data. To reduce the risk of attribute disclosure, cell counts less than or equal to 5 will be suppressed.

29. Declaration of interests

The Principal Investigator declares no conflict of interest.

30. Dissemination policy

The protocol will be submitted for publication on an open access basis. The study results will be submitted for publication on an open access basis. A lay summary of the study findings will be produced and disseminated to study participants who indicated on their consent forms that they wished to receive a copy of study findings. Briefing notes will summarise study findings for recruiting organisations and policymakers.

ICMJE authorship guidelines will be followed.

Public access to the participant-level dataset is not planned.

References

- UN General Assembly. Protocol to Prevent, Suppress and Punish Trafficking in Persons, Especially Women and Children, Supplementing the United Nations Convention against Transnational Organized Crime. 2000 [Available from:
- https://www.refworld.org/docid/4720706c0.html.
- 2. Walk Free Foundation. Global Slavery Index. Australia: Walk Free Foundation; 2018.
- 5. Helen Bamber Foundation. Addressing mental health needs in survivors of modern slavery: a critical review and research agenda. London; 2016.

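### Section 27 has participants told that their responses are anonymous, but the protocol keeps them pseudonymised and linkable to the person

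*Protocol*

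**What the plan says.** Protocol section 27 (Consent) sets out what is said during the formal consent process: "each participant will be informed that their responses will be anonymous and confidential". A parenthesis gives examples of what is meant: "no names would be used on questionnaires, and questionnaires will not be seen by anyone outside the study".

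Section 28 (Confidentiality and anonymity) uses another term: "The information provided by participants will be confidential and pseudo-anonymised". It adds that "All participants will be assigned a unique PIN" and that identifying details are held apart from the research data. It also says that the limits of confidentiality are set out in the information sheet and discussed with every participant at consent.

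Section 18h says of the number generated after the T1 interview: "The PIN should be written in ink at the top of all sheets in the questionnaire pack". Section 18i lists among the retention measures: "Asking participants to complete a contact details information sheet at baseline". Section 19b says that routine NGO data "will be extracted by The Salvation Army for participants who have provided their consent". Section 19c limits access to personal data to a named set of groups and allows one exception, for serious risk of harm, in which the researcher will "explain to the participant that they need to break confidentiality to respond to the identified risk".

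**The concern.** Anonymous data cannot be traced to the person who gave them. Pseudonymised data carry a code in place of a name and can be traced by whoever can connect code and person. Sections 27 and 28 apply one term each to the same answers, and only one can be right. The one that conflicts with the rest of the protocol is the one participants are to hear.

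This matters because of who the participants are and what they are asked. They are survivors of trafficking. The interview covers distress, perceived safety and risk of harm, and at T1 (and usually T2) it is conducted by a trained staff member of the NGO supporting them. What they are told about identifiability at consent should be accurate, whether or not any individual would answer differently.

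**Working it through.** No arithmetic applies and there is no figure to reproduce. The check is whether the procedures in the protocol could run on anonymous responses.

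| Procedure | Protocol section | Must answers be traceable to a person? |
|---|---|---|
| The NGO researcher who conducts T1 completes the registration form that generates the number, which then goes on every sheet | 18a, 18h | Yes: the interviewer knows both person and number |
| Contact sheet at baseline, with a trusted person's telephone number | 18i | Yes, once combined with repeat interviews of the same person |
| Interviews at T1, T2 and T3; the primary outcome is within-person change in CORE-OM | 8, 12, 13, 20a | Yes: paired scores must belong to one known person who is contacted again |
| Support records extracted for each consenting participant and entered in the study database to build the dose measure | 12, 19b, 20b | Yes: dose is joined to each person's change score |
| Withdrawal of data from analysis on request to the principal investigator | 18j | Yes: the request must be matched to that person's data |
| Purposive selection for the qualitative study after T1, then contact by post and telephone | 15 | Yes: a study record leads to a named individual |
| Acting on a disclosure of serious risk | 19c, 28 | Yes: the discloser is known |

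Every row needs re-linkable data. Section 28's term therefore describes the design, and section 27's does not.

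Section 27 also shows the difference within its own text. For people who decline, it provides for anonymous collection of gender, age and country of origin. No follow-up or linkage is planned for those data, so there the word can be true. For participants it cannot.

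The secondary point concerns the access list. Section 19c names the study team (including NGO researchers and Clinical Trials Unit staff), interpreters, transcribers and auditors, and treats risk disclosure as the sole exception. Under section 19b The Salvation Army extracts records for those who consented. To do so it must know who they are. It may already hold the underlying client records, since it manages the Victim Care Contract, but knowing that a given client is in the study is additional. It is not on the list. This inconsistency stands by itself and is not evidence for the main point.

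**The case against.** The best defence is that the sentence should be read whole. Its parenthesis illustrates the assurance by names being left off questionnaires and by restricted viewing, and section 19b repeats that no names go on them. Participants therefore hear more than the bare word. This is fair, but what the parenthesis describes is coding, which is what section 28 calls pseudo-anonymised.

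Second, the limits of confidentiality are covered. Section 28 commits to discussing them with everyone, and section 19c says the serious-risk exception is in the information sheet. This stands, and it removes much of the possible harm. It does not settle the wording: confidentiality concerns who may be told, and anonymity concerns whether anyone can know who answered. A participant could be given both messages, and they do not agree.

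Third, participants will see for themselves that they are known. They sign a consent form and give contact details. The information sheet is to state that there are three questionnaires and that they may be approached for a further study, and records are extracted only with consent. NGO researchers who are caseworkers may not take consent from or interview their own clients (section 15). The King's College London researcher administers T3, and T2 for those who have left the recruiting organisation (section 18a). All of this stands.

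A reader might therefore go further and infer that consent is invalid, that survivors will disclose more than they otherwise would, or that use of the linked dose records is undermined. The protocol does not support those readings: it shows substantial disclosure alongside one untrue word, and the information sheet and consent form, which would be needed to judge, are not available.

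**Conclusion.** The contradiction is real and lies in the current text. The assurance of anonymity in section 27 is untrue for cohort participants, and section 28 gives the accurate description. It reaches every one of the 450 planned participants (section 14), because it is part of the formal consent process.

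Its weight is that of an inaccurate statement to a vulnerable group, worth correcting because the correction is easy. It is not a fault in the data safeguards: coding, separate storage, restricted access and small-cell suppression are not in question. There is no numerical bias and no effect on the estimate, power or handling of missing data.

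The conclusion assumes that consent-takers will say what section 27 says they will. If the information sheet and consent form already describe coded, linkable data, the correction is confined to the protocol. The omission of The Salvation Army from section 19c is a smaller, separate inconsistency.

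**What to change.** In section 27, replace the word *anonymous*, as applied to participants' responses, with wording such as: pseudonymised (stored under a study number that the study team can link to the participant, to later interviews and to NGO records) and confidential within the stated limits. Keep the examples about names and viewing, which are then correctly placed. The word can stay for the details collected from decliners. Check the information sheet and consent form, including translations, and make the same change wherever they repeat the word.

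In section 19c, add The Salvation Army to the access list, limited to the identifiers needed to extract the records of consenting participants.

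The cost is a wording amendment with notification to the ethics committees. Some participants may answer slightly more guardedly once told that their answers are coded and not anonymous. Sample size, schedule and analysis do not change.
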